MIFE has a rapid onset of action and achieves peak plasma levels within 1 - 2 hrs of oral dosing. Peak plasma levels and bioavailability increase as a function of dose but are not directly proportional to dose. However, plasma concentrations of MIFE metabolites do increase in direct proportion to dose; metabolites have antiglucocorticoid activity and contribute to long-acting drug effects (Pomara et al., 2002). MIFE is effective with once-a-day dosing. The half-life is 40 hrs following a single dose and 84.6 hrs following multiple doses. Following discontinuation of MIFE, plasma levels are detectable for up to 2 weeks (Heikinheimo et al., 2003). For this study, we selected to use the high MIFE dose of 1200mg, based on recent clinical trials for other neuropsychiatric disorders associated with HPA-axis dysfunction, and that 1200 mg MIFE has been safely administered over extended periods (MIFE Investigator Brochure, Corcept Therapeutics). This study only exposes subjects to MIFE for up to 6 days. We are not planning to reduce MIFE dose during such a brief treatment period. If a subject experiences significant medication side-effects or any serious adverse event or if the participant declines to continue medication, then we will discontinue that participant from the study. It

should be noted that inpatient subjects are under continuous nursing observation throughout the CRU stay and thus adverse events can be identified and addressed rapidly. HC subjects will be instructed to call the study doctor if they have any adverse events. Subjects will be randomized to active MIFE and placebo on a 2:1 ratio.

In the proposed study, MIFE will be administered under an IND ([name] 124365). MIFE (300 mg) and matching placebo will be provided by Corcept Therapeutics, Menlo Park, CA. We will overencapsulate the medication and placebo as necessary. The Johns Hopkins Bayview Investigational Drug Services (IDS) will maintain the inventory and dispense the medication. MIFE absorption and elimination are not affected by age, body weight, BMI, race or sex (Mifepristone Investigator Brochure, Corcept Therapeutics).

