Each subject will participate in an initial assessment, and a possible second assessment visit for completion of medical history, vital signs and laboratory tests. AUD participants will be admitted to the CRU for 6 nights. HC participants, who participate in the study on an outpatient basis, will continue MIFE dosing and salivary sample collection at home. For AUD participants, there are two follow-up visits at 1 and 2 weeks following CRU discharge. For HC participants, there is one follow-up visit at 1 week following the second fMRI. It is anticipated that subjects will complete all study procedures within a 6 month period.

c. Blinding, including justification for blinding or not blinding the trial, if applicable.

Staff and subjects will be blind to the alcohol and MIFE doses administered during this study to reduce expectancy effects.

d. Justification of why participants will not receive routine care or will have current therapy stopped.

Subjects are not seeking treatment for their AUD; they will not currently be engaged in therapy.

e. Justification for inclusion of a placebo or non-treatment group.

A placebo MIFE dose is included for comparison with the active drug effects and to control for expectancy effects.

f. Definition of treatment failure or participant removal criteria.

A participant will be removed from the study if s/he experiences a moderate or severe adverse event, is noncompliant with study or CRU rules, or if it is determined by the study physician to be unsafe to continue.

g. Description of what happens to participants receiving therapy when study ends or if a participant's participation in the study ends prematurely.

MIFE dosing is discontinued at the time of discharge from the study.

5. Inclusion/Exclusion Criteria

Healthy, non-treatment seeking, 21-60 years old, male and female subjects will be recruited through the media. Recruitment uses a mix of newspaper, radio, and on-line advertisements. Based on the 2011 census, the Baltimore metropolitan area is mostly Caucasian (61%) or African-American (30%); the remaining 9% is Asian (4%) and persons reporting two or more races (5%); 8.8% of the population report Hispanic ethnicity.

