Aim 3. AMR variables include: total number of alcohol drinks earned; total number of responses during the 60-minute session; distribution of responses for alcohol versus money; progressive ratio breakpoint for alcohol (maximum completed ratio value); response rate (responses/min) and response latency to compete the ratio for alcohol and money. We also measure alcohol craving using the Tiffany Craving Scale; these data will be summarized using peak score and area under the curve. The normality of the outcome measures will be examined first and two sample t-test, or equivalent non-parametric methods will be used to compare the outcomes between GR antagonist-treated group and placebo-treated group.

Aim 4: Subjective and physiological data will be collected repeatedly during the alcohol sensitivity session. We will test outcome measures between the two groups using mixed-effect linear regression with random intercept. Baseline measures will be examined as potential confounding factors and added to the model if needed. We will summarize the baseline adjusted area under the curve and peak values of the outcome measures and compare between the two groups using repeated measure ANCOVA model.

Aim 5: We use the SAFTEE to collect comprehensive side-effect information. We will construct negative binomial generalized linear regression model with the number of events as the dependent variable and grouping and other covariates as independent variables. The model will give the difference in the logs of expected numbers of side effect events between the two treatment groups. We will then also make comparisons taking into consideration the duration and severity of the side effects, which are both collected in SAFTEE for each reported side effect event. A summary side-effect score will be calculated as the sum of the duration multiplying the severity of each side effect event.

Secondary analyses: Another objective of this study is to generate power estimation for a full-size future clinical trial.

d. Early stopping rules.

Individual subjects will be discontinued from the protocol if they experience a moderate-to-severe adverse reaction to MIFE. They also will be discontinued for repeated rule violations on the CRU. The study will be discontinued if there is a pattern of MIFE-related AEs or SAEs.

8. Risks

a. Medical risks, listing all procedures, their major and minor risks and expected frequency.

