MIFE has been shown to infrequently cause low blood potassium (hypokalemia) in patients with Cushing Syndrome. Symptoms of low potassium may include muscle weakness, aches, or cramps, abnormal or irregular heartbeats (palpitations). Although hypokalemia has not been observed in other patient populations, we will exclude subjects with potassium levels below the normal range at screening or day 1.

MIFE administration also has been associated with the possibility of developing a rash and/or a dry mouth. Both side effects are mild-to-moderate in severity and both have been found to discontinue when drug administration is terminated.

Use of MIFE with strong CYP3A inhibitors is counter indicated, as concomitant use can increase mifepristone plasma levels. Subjects using CYP3A inhibitors in last 3 months are ruled out prior to study enrollment.

Alcohol administration: Alcohol may produce mood and behavioral effects that are dysphoric and that can result in impairment in performance and judgment and, in cases of overdose, ethanol can produce medically serious toxic effects. Prior to the fMRI on day 1, subjects receive an alcohol drink in a standardized calorie-free mixer targeting a blood alcohol level of 80mg% based on gender and BMI. Following the Alcohol Motivated Responding Session, during the alcohol self-administration period, the maximum dose of alcohol that subjects can self-administer is five standard drinks over 50 minutes; this dose will produce a blood alcohol level of approximately 120mg/dL. In the alcohol sensitivity session, the proposed alcohol dose is one that produces a blood ethanol level of approximately 100 mg/dL. Study subjects are those who regularly drink doses of alcohol greater than the amount used in this study, reducing the likelihood of serious adverse events. These are medically safe but behaviorally intoxicating levels, associated with impairment of psychomotor and cognitive performance and with emotional and behavioral effects that may range from sedation and drowsiness to agitation, irritability, depression, and emotional lability. These effects dissipate as blood ethanol levels decline.

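### The Aim 5 duration-times-severity score can rank a short severe event below a long mild one, and the removal rules can lower it further; compare highest severity per subject instead

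*Combined protocol and SAP*

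**What the plan says.** Section 7c, Statistical Analyses, Aim 5 begins with event counts: "We will construct negative binomial generalized linear regression model with the number of events as the dependent variable and grouping and other covariates as independent" (that is, as predictors). A second step follows: "We will then also make comparisons taking into consideration the duration and severity of the side effects". Both features are recorded in SAFTEE, event by event. Only one such summary is then specified: "A summary side-effect score will be calculated as the sum of the duration multiplying the severity of each side effect event". The plan gives no numeric codes for the severity grades, no unit for duration, and no rule for an event still running when a subject leaves.

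Removal is described in three places, with three different triggers:
- Section 4f: "A participant will be removed from the study if s/he experiences a moderate or severe adverse event".
- Section 7d: "Individual subjects will be discontinued from the protocol if they experience a moderate-to-severe adverse reaction to MIFE".
- Section 4a, MIFE Administration: "If a subject experiences significant medication side-effects or any serious adverse event or if the participant declines to continue medication", the participant is discontinued.

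SAFTEE is given daily on the CRU (section 4a, General CRU procedures) and by video call on days 2 and 3 for healthy controls. Discontinued subjects are asked to complete the post-discharge follow-up (section 4a, MIFE Administration). SAFTEE is repeated at each follow-up visit (section 4a, Discharge and Follow-up). Table 1 places these visits on days 14 and 21 for AUD subjects and day 11 for controls.

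**The concern.** Adverse events and side effects stand first among the primary outcomes in section 7a, and section 9 justifies the trial largely by the safety information it will yield. The count model treats every event alike, so the score is the only specified between-arm summary in which severity plays a part.

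A product of duration and severity lets days compensate for grade. The subjects with the higher grades are also the ones whom sections 4f and 7d take off the drug and out of daily assessment. If their events are then shorter, or are recorded as shorter, the score falls for the subjects who fared worst. An arm with more such events could look no worse, or even better, than an arm with persistent mild complaints.

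**Working it through.** **The plan's own figure.** The only Aim 5 figure is 22 subjects per group (section 7c, Power analyses). It concerns Poisson event counts with a mean of 12 on MIFE, not the score. No comparator mean is given, so it can be neither reproduced nor refuted, and it does not bear on this point. The plan states no figure for the score.

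**Inputs.** From the documents: the score formula (section 7c); dosing over 6 days for AUD subjects and 4 days for controls (Table 1). Assumed, because the plan is silent: duration in whole days; mild = 1, moderate = 2, severe = 3, with severe varied from 2 to 4.

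**Step 1: condition for reversal.** An event of duration d and severity code s contributes d × s. A mild event outscores a severe one when d(mild) × s(mild) > d(severe) × s(severe), that is, when d(mild)/d(severe) > s(severe)/s(mild). With codes 1 and 3 the mild event must last more than three times as long.

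**Step 2: illustration with codes 1, 2 and 3.**

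| Event | Score |
|---|---|
| Mild, 6 days | 1 × 6 = 6 |
| Moderate, 1 day | 2 × 1 = 2 |
| Severe, 1 day | 3 × 1 = 3 |
| Severe, 2 days | 3 × 2 = 6 |
| Severe, 3 days | 3 × 3 = 9 |

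Six mild days outscore one severe day, tie with two, and lose to three.

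**Step 3: how often the condition is met.** Counting all whole-day pairs of one mild and one severe event, strict reversals are:

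| Severe code | 4-day horizon | 6-day horizon |
|---|---|---|
| 2 | 2 of 16 | 6 of 36 |
| 3 | 1 of 16 | 3 of 36 |
| 4 | 0 of 16 | 2 of 36 |

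With severe = 3, longer horizons give 26 of 196 (14 days) and 57 of 400 (20 days). These counts weight all duration pairs equally and are not probabilities. If severe events are typically brief, the relevant cases are those with a one-day severe event. Over 6 days with severe = 3, mild events of 4, 5 or 6 days then outscore it (3 of 6); the figure is 4 of 6 with severe = 2 and 2 of 6 with severe = 4.

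**Step 4: effect of removal.** Suppose a severe event would run 5 days: 3 × 5 = 15. If it is recorded for one day only, it scores 3 × 1 = 3. Against six mild days (6), the order switches. There are two routes to the shorter figure: the event really ends sooner because the drug is stopped, or its end date is lost or cut at removal. By the first route the score is accurate about time but mixes drug toxicity with the removal rule. By the second it is wrong. The plan has no rule that separates the two.

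**The case against.** The strongest case against runs as follows. Severity multiplied by time is a legitimate measure of cumulative burden, and a preference for peak severity is partly a matter of choice. Reversal is conditional, and on the equal-weight counts it is uncommon. Removal does not by itself stop recording, because follow-up SAFTEE is planned. Exposure does not end at once either: section 4a, MIFE Administration gives half-lives of 40 and 84.6 hours after single and multiple doses (section 8a uses 18 hours when setting contraception, so the documents are not uniform). The score supplements the count model, and severe events would also surface through the study stopping rule in section 7d and the event reporting in section 8c.

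Most of this stands, and it limits the point. What it does not remove is that the count model carries no severity information, so it cannot correct the score's ordering. Follow-up attendance is requested rather than assured, and the first AUD visit is on day 14, so end dates after an early removal may rest on recall.

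A reader might infer more than the documents allow:
- That a long mild complaint always outweighs a short severe one. It does so only above the duration ratio in Step 1, and the plan's codes are unknown.
- That removal is shown to shorten the worst events. Section 8a says of rash and dry mouth that "both have been found to discontinue when drug administration is terminated", but it calls both mild to moderate and says nothing of severe reactions. A one-day resolution is an illustration only.
- That the safety comparison is biased towards no harm. No arm-level calculation shows this, and none is possible without event rates and durations by grade.

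**Conclusion.** The weakness is real but bounded. The only specified severity-based comparison can place a short severe event below a long mild one, and sections 4f and 7d create a plausible route by which subjects with moderate or severe events accrue less score. Followed as written, the comparison can therefore understate harm in the arm that causes such events.

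The size is unknown. The numbers above rest on assumed severity codes and day units and show single-event arithmetic, not an arm difference. The event-count model is unaffected by this choice of score. The change is still worth making before unblinding, because this is a safety outcome and the remedy uses data already collected.

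**What to change.** Amend section 7c, Aim 5, using the same SAFTEE records:

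1. Make the severity comparison the highest recorded severity per subject (none, mild, moderate, severe), tested between arms by an exact rank test or a proportional-odds model. Shortened durations do not affect it.
2. Add the proportion per arm with at least one moderate or severe event, with an exact confidence interval.
3. Report removals for adverse events by arm as a separate line. Do not recode them as the worst grade: under section 4f every moderate event leads to removal, so recoding would empty the moderate category.
4. Summarise duration by severity grade.
5. Keep the duration-times-severity score only as a supportive burden measure, and state its severity codes, its duration unit and a rule for events ongoing at removal.

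The removal triggers in section 4a (MIFE Administration), section 4f and section 7d differ and must be reconciled. Which of them should apply is for the investigators to settle.

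The cost is SAP wording and one or two extra analyses, with no new data. The drawback is that the single continuous score becomes supportive.

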Initial assessment findings will be reviewed and those participants who still appear to be eligible for study participation will be invited to come to the research office for blood work, urine toxicology and a medical history and vital signs. A urine toxicology screen is obtained to check for recent drug use. Women will complete urine pregnancy testing. Subjects will undergo a medical history, and standard laboratory tests (complete blood count, comprehensive metabolic panel) and a 12-lead ECG. In rare cases, MIFE can cause low blood potassium and cardiac changes. We will exclude individuals with potassium levels below the normal range or who have any clinically significant abnormality on the ECG. The ECG and medical records will be reviewed by the study physician ([name]). Psychiatric and behavioral assessments will be reviewed by [name], Co-PI and a licensed psychologist. We are eliminating all sections of the brief physical examination (PE) from the protocol except vital signs to enhance safety for staff nurse and physician. We have determined that the PE findings have never contributed to ruling out participation by participant. The detailed medical history will be obtained. We expect to assess 3 people for each eligible participant; thus the total assessed sample will be 450 subjects. Because of the risk of confounding by smoking rates and severity among AUD subjects, we will recruit an equal number of HC smokers, matched on Fagerstrom scores.

General CRU procedures:

For AUD subjects, this study will be completed as a 7 day (6 night) inpatient protocol on the Bayview Clinical Research Units (CRU). We will conform with all COVID-related safety procedures implemented by the CRU.

On Day 1 prior to completion of any study procedures, subjects will undergo a urine toxicology for recent alcohol and drug use; a drug positive other than marijuana will result in rescheduling study procedures. Female subjects will complete a urine pregnancy test; positive subjects will be excluded from further study procedures. Vital signs (BP and HR) and laboratory tests (CBC and CMP) will be obtained. Updated assessment measures will include an interim timeline follow-back of alcohol use.

During the Bayview CRU stay, participants will be allowed to smoke; subjects will be smoking abstinent for 2 hours prior to study procedures. They will have the option to receive a transdermal patch (21 mg) while off the CRU to complete study procedures.

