Daily at 8:00 pm, participants will complete self-reports of alcohol craving, including Visual Analog Scale for alcohol and tobacco craving (VAS); Penn Alcohol Craving Questionnaire (PACS) (Flannery et al., 1999), Beck Depression Inventory-II (BDI-II), Beck Anxiety Inventory (BAI), Obsessive Compulsive Drinking Scale (OCDS), and Alcohol Urge Questionnaire (AUQ). Nursing staff will complete clinician-administered instruments for alcohol withdrawal assessment (see below). Participants will have PRN access to over the counter medications to treat headache, gastrointestinal upset and body aches.

Each day of the CRU stay, the CRU nurse will administer the Systematic Assessment for Treatment of Emergent Events (SAFTEE) (Johnson et al., 2005). This standardized, structured

instrument is specifically adapted for use in substance use disorder clinical trials, to collect information on incidence and severity of medication side effects and adverse events.

To determine if the degree of elevation of CORT in response to GR blockade by MIFE correlates with any of our outcome measures, each morning upon wakening and at bedtime on the CRU, a salivary cortisol sample is obtained. Baseline samples will be collected on day 1, prior to beginning study medications. Measurement of CORT in saliva is not invasive and multiple samples per day are easily obtained. Unlike serum CORT, salivary CORT is unbound to protein and reflects the physiologically relevant fraction. For each sample, subjects chew a pad for 90 sec, which they then place into a capped salivette. Saliva is harvested by centrifugation and stored in a cryotube at -70 until assayed in duplicate (Diagnostic Systems Laboratories; Webster, Texas). The intra- and inter-assay coefficients of variation are below 5%. As we expect variability in CORT within and across MIFE doses, these data will be included in our analyses.

Because MIFE is occasionally associated with hypokalemia, serum potassium level is obtained before study procedures on day 1 and again on day 7 and at the 1 week follow-up visit. Potassium replacement will be addressed as needed.

Outpatient procedures for HC: Healthy control subjects will complete the study as a 4-day outpatient protocol.

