This study will include two groups of participants – persons with AUD and healthy controls. AUD subjects will have a current DSM 5 alcohol use disorder and will be actively drinking at least 50% above NIAAA recommended guidelines (women >10 drinks/week and men >20 drinks/week) and at least 5 binge drinking episodes in the past 30 days. Recent heavy drinking will be confirmed by PEth blood spot analysis ≥ 50 ng/mL. HC subjects will not meet DSM 5 criteria for AUD and will not be drinking above NIAAA recommended guidelines as confirmed by PEth blood spot analysis < 50 ng/mL. We expect to consent 450 subjects in order to accrue 150 subjects into the study procedures (N=75 for AUD and N=75 healthy controls). Historically, our retention in the CRU has been outstanding, with over 90% of subjects completing the protocol.

Additional Inclusion Criteria for all subjects:

- Nontreatment seeking volunteers;
- 21 – 60 years old;
- English speaking;
- 5th grade literacy to ensure ability to read study assessment instruments;
- no current serious psychiatric or health problems that would contraindicate study participation;
- BMI > 19 and < 40 ; medication dosing is not weight-adjusted. We have restricted the weight range of participants to reduce weight-associated variability;
- For women, negative urine pregnancy test prior to initiating MIFE treatment and agreement to use nonhormonal birth control for 2 weeks following last MIFE dose. A medical record of surgical sterilization or elevated FSH level confirming post-menopausal status is required to document non-childbearing potential;
- No adult seizure history;
- No serious alcohol withdrawal complications in prior alcohol withdrawal episodes;

- Some non-drinking days on 90-day TimeLine Followback Drinking Calendar;
- Study Physician and PI recommendation.

Exclusion criteria for all subjects:

- Women on hormonal birth control, or who are pregnant, nursing or planning pregnancy; women with unexplained vaginal bleeding;
- Current DSM 5 mood, anxiety or psychosis diagnosis or currently treated with psychiatric medication;
- Current substance use disorder except alcohol, marijuana (mild) or tobacco; current illicit drug use other than marijuana;
- History of serious alcohol withdrawal symptoms (e.g., seizures, hallucinations) or history of inpatient, medicated alcohol withdrawal management, and CIWA-Ar score at time of assessment ≥ 12 ;

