- Elevation of aspartate aminotransferase or alanine aminotransferase exceeding 5 X the upper limit of normal;
- History of clinically significant ECG abnormality or cardiovascular illness;
- Potassium levels below normal range at screening or CRU admission;
- Use of CYP3a inhibitors in the 3 months prior to study participation, including simvastatin, lovastatin, and CYP3A substrates with narrow therapeutic ranges, such as cyclosporine, dihydroergotamine, ergotamine, fentanyl, pimozide, quinidine, sirolimus, and tacrolimus; itraconazole, nefazodone, ritonavir, nelfinavir, indinavir, atazanavir, amprenavir, fosamprenavir, boceprevir, clarithromycin, conivaptan, lopinavir, posaconazole, saquinavir, telaprevir, telithromycin, or voriconazole; midazolam, triazolam, sildenafil;
- Any illness, condition, or medication use known to interact with MIFE metabolism (as outlined in the FDA package insert) that, in the opinion of the study investigators and the admitting physician, would preclude safe and/or successful study completion;
- History of metal implantation that would preclude MRI scanning, including implants, pumps, pacemakers.

6. Drugs/ Substances/ Devices

- a. The rationale for choosing the drug and dose or for choosing the device to be used.

Mifepristone. MIFE has been developed by Corcept Therapeutics and is currently FDA-approved or under investigation for hormone sensitive tumors and various neuropsychiatric disorders. MIFE acts as an antagonist at GR and progesterone receptors (PR) (DeBattista and Belanoff, 2006). We are examining effects of MIFE 1200 mg and matching placebo. This MIFE dose has been safely used over extended administration in humans. In our pilot data, we observed an effect of this dose on subjective responses to alcohol administration. MIFE has demonstrated a strong safety profile in severely medically compromised patients with Cushing Syndrome, suggesting that it will be well tolerated in clinical populations with less morbidity. Indeed, very few adverse experiences have occurred in clinical trials with diverse psychiatric populations, including AUD, bipolar, schizophrenia and dementia patients (Yarabas and Pogun, 2011; Watson et al., 2012; Howland, 2013; Morgan and Laufgraben, 2013; Mason, 2014). At present, the most clinically significant barrier to MIFE use is that it cannot easily be used in women on hormonal birth control.

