Mifepristone (MIFE) Administration: Since MIFE blocks the progesterone receptor, treatment of a pregnant woman would result in the termination of pregnancy. All females must have a negative urine pregnancy test prior to MIFE initiation; women on hormonal birth control, who are pregnant, nursing or planning pregnancy, and women with unexplained vaginal bleeding are excluded from study participation. In addition, women must agree to use a non-hormonal form of birth control for at least 1 month after stopping MIFE treatment. We will provide female participants with condoms at each outpatient follow-up visit. Women may experience endometrial thickening or unexpected vaginal bleeding; there is a low likelihood of these events.

Due to the anti-progestin effects of mifepristone and given the lack of adequate data on the potential levels of mifepristone in semen, male subjects will be required to employ barrier protection with their female partners. Males should use barrier protection during intercourse for at least 5 half-lives of the drug (half life = 18 hours) plus 90-days (the duration of one spermatogenic cycle in men and residence time for unejaculated sperm) after last dose of mifepristone to avoid risk of anti-progestin effects transmitted to female sexual partners. We will provide male participants with condoms for at least 94-days after the last dose of mifepristone.

Based on prescribing information for MIFE treatment of Cushing Disease, MIFE may produce prolongation of the QT interval of the electrocardiogram (ECG) and use of MIFE with QT interval-prolonging drugs is contraindicated. A recent evaluation of the cardiac safety of three doses of 1200 mg MIFE given every 12 hrs to subjects found no clinically meaningful QT prolongation in healthy subjects (Corcept Therapeutics Investigator Brochure).

Based on data in individuals with Cushing Disease, MIFE may cause adrenal insufficiency. Symptoms of adrenal insufficiency may include abdominal pain, vomiting, muscle weakness and fatigue, depression, extremely low blood pressure (hypotension), weight loss, changes in mood, and shock (adrenal crisis). There has been no evidence of the development of adrenal insufficiency during short-term administration of MIFE doses up to 1200 mg in clinical trials for other psychiatric disorders.

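### The protocol calls QT interval-prolonging drugs contraindicated with mifepristone, but neither excludes them as a class nor prohibits them during dosing

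*Combined protocol and SAP*

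**What the plan says.** Section 8a (Mifepristone Administration) reports, from the prescribing information for Cushing disease, that mifepristone may lengthen the QT interval and that "use of MIFE with QT interval-prolonging drugs is contraindicated". It then cites an evaluation of three 1200 mg doses given 12 hours apart, which "found no clinically meaningful QT prolongation in healthy subjects".

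The same section also treats strong CYP3A inhibitors as contraindicated, and there it states the consequence: "Subjects using CYP3A inhibitors in last 3 months are ruled out prior to study enrollment". Section 5 carries this through with an exclusion for "Use of CYP3a inhibitors in the 3 months prior to study participation", followed by a list of named drugs.

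The other parts of the plan that bear on co-medication or cardiac risk are:

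- Section 5, catch-all exclusion: "Any illness, condition, or medication use known to interact with MIFE metabolism (as outlined in the FDA package insert"), applied where the investigators and admitting physician think it would prevent safe or successful completion.
- Section 5, inclusion criteria: "Study Physician and PI recommendation".
- Section 5, exclusion of current psychiatric medication, and of a history of significant ECG abnormality or cardiovascular illness.
- Section 4a, Assessment: "We will exclude individuals with potassium levels below the normal range or who have any clinically significant abnormality on the ECG".
- Section 4a, General CRU procedures: "Participants will have PRN access to over the counter medications to treat headache, gastrointestinal upset and body aches".

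**The concern.** The risk section names a drug class that must not be combined with the study drug, yet the operative parts of the protocol contain no rule that keeps it out. Whoever screens subjects works from section 5, and a person taking a QT interval-prolonging drug can satisfy every specific criterion there. Whether that person is enrolled then turns on case-by-case recognition by the physician or investigator.

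The stake is subject safety. The gap continues after enrolment, because no rule covers drugs started during dosing. Healthy controls take mifepristone at home. Their calls on days 2 and 3 cover the side-effect instrument, an adrenal insufficiency questionnaire and observed dosing, with no co-medication check stated. AUD subjects may have over-the-counter products as needed on the unit, again with no stated QT check. Those products are not named, so this shows that a rule is missing and not that one is breached.

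**Working it through.** **1. The two contraindications side by side**

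| Step | Strong CYP3A inhibitors | QT interval-prolonging drugs |
|---|---|---|
| Called contraindicated (section 8a) | Yes | Yes |
| Exclusion stated alongside (section 8a) | Yes, use in last 3 months | No |
| Own criterion in section 5 | Yes, with named drugs | No |
| Precaution in section 8b | None beyond the exclusion | None |

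The mifepristone precautions in section 8b deal with pregnancy and contraception, vaginal bleeding, potassium and adrenal insufficiency. None concerns QT or co-medication.

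**2. Could another criterion do the job?**

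- The psychiatric-medication and CYP3A exclusions may remove some QT interval-prolonging drugs, but for other reasons. They do not cover the class.
- The catch-all is limited to interaction with mifepristone metabolism. Section 8a describes an effect on the ECG. Even read broadly, the clause depends on opinion.
- The ECG, cardiovascular and potassium exclusions screen the subject's condition before any mifepristone, not what the subject is taking.
- The general statements in section 8b that ineligible subjects are not enrolled refer back to criteria that have no such item.

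**3. Is there an ECG on drug?** The procedures describe a 12-lead ECG at screening only. Section 7a names ECG among the cardiovascular outcomes of the alcohol sensitivity session on day 6, but the description of that session in section 4a lists heart rate, blood pressure, skin conductance and skin temperature, and no ECG. Healthy controls have no such session.

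**4. Scale, under an assumption.** The documents give no rate of use. Let *s* be the share of enrolled subjects on a QT interval-prolonging drug that no other criterion catches. Inputs: 150 enrolled (section 5), 2:1 allocation to mifepristone (section 4a, MIFE Administration), 3 people assessed per eligible participant (section 4a, Assessment).

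Subjects = 150 × *s*; exposed to mifepristone = 150 × *s* × 2/3; assessments to replace them = 150 × *s* × 3.

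| Assumed *s* | Subjects | Exposed | Extra assessments |
|---|---|---|---|
| 1% | 1.5 | 1 | 4.5 |
| 3% | 4.5 | 3 | 13.5 |
| 5% | 7.5 | 5 | 22.5 |

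Dosing lasts 4 days in healthy controls and 6 days in AUD subjects.

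**5. How long a prohibition might need to run.** The protocol states three half-lives. Five half-lives, in days, is 5 × *h* / 24:

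- 18 h (section 8a, male contraception text): 90 h = 3.75 days
- 40 h (section 4a, after a single dose): 200 h = 8.3 days
- 84.6 h (section 4a, after multiple doses): 423 h = 17.6 days

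Section 4a also says that plasma levels are detectable for up to two weeks after stopping.

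**The case against.** The strongest reply is that the protocol is reporting a label statement written for patients with Cushing disease, and that the healthy-subject evaluation is reassuring. That evaluation gave 1200 mg every 12 hours, twice this study's daily rate. This stands as far as it goes, but it was three doses against four or six here, and the protocol does not say that it addressed co-medication.

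Second, there are real safeguards: a detailed medical history, physician review of the ECG and medical records, the exclusions for low potassium and cardiovascular illness, a general criterion against health problems that would contraindicate participation, continuous nursing observation and six-hourly vital signs for AUD subjects, and video-observed dosing for controls. Sections 4f and 7d remove subjects with moderate or severe adverse events, and section 4f also removes those judged unsafe to continue. The catch-all refers to the package insert, which could lead an investigator to the QT warning. These make admission of a contraindicated subject less likely. Each is either judgement without a stated rule, a screen of something other than co-medication, or a response once a problem has appeared.

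Third, the 1% to 5% range has no source in the documents, and in a healthy population aged 21 to 60 the true share could be zero. That is fair. The range only gives scale, and the finding does not depend on it. Nor does it depend on the half-life discrepancy, which matters only for setting how long the prohibition lasts.

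**Conclusion.** The concern holds. The contraindication in section 8a has no counterpart in section 5, in screening, in the precautions of section 8b or in any rule for the dosing period, whereas the parallel CYP3A contraindication is turned into an explicit exclusion. Followed as written, section 5 can admit a subject whom the protocol itself calls contraindicated, unless a clinician notices.

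The size is modest and not known from the documents: about 1 to 5 subjects given mifepristone if 1% to 5% of those enrolled use an uncaught drug, and possibly none. No sample size, power or analysis figure is affected. Existing safeguards lower the risk but do not replace a co-medication rule. The change should be made, because it closes a stated safety gap at little cost.

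**What to change.** - Add to section 5 a separate exclusion for current use of QT interval-prolonging drugs, independent of the wording about mifepristone metabolism, with the washout set by the study clinicians.
- Prohibit these drugs during dosing, including among the as-needed products on the unit. Have the clinicians state how long after the last dose this applies, once they have settled which half-life in sections 4a and 8a is correct.
- Ask about these drugs at the screening medical history and again at the day 1 updated assessment, before randomisation.

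The cost is one eligibility line, one dosing-period line and a question at two assessments that already take place. The downside is some additional screen failures. Under the same 1% to 5% assumption, replacing these subjects needs about 5 to 23 further assessments on top of the planned 450.
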